7.3.5 EARLY TERMINATION VISIT

Should early termination be deemed necessary (following procedures detailed above), and the situation does not involve a need for immediate hospitalization of the participant, then the participant will be invited to an early termination visit in which the full typical debriefing interview (i.e., risk assessment and referral as appropriate) will be conducted.

7.3.6 UNSCHEDULED VISIT

There will be no unscheduled visits. Should a participant present at the laboratory at the wrong time, a member of the study staff will reschedule the visit if needed or refer her to her mental health provider as appropriate.

7.3.7 SCHEDULE OF EVENTS TABLE

Procedures	Screening	Enrollment/Baseline	IDS RANDOMIZATION	Follow-Up (Condition 1, Visit 1)	Follow-Up (Condition 1, Visit 2)	Follow-Up (Condition 1, Visit 3)	Follow-Up (Condition 2, Visit 4)*	Follow-Up (Condition 2, Visit 5)*	Follow-Up (Condition 2, Visit 6)*	Final Visit/ Debriefing Visit
Informed Consent	Verbal	Written								
	х	х								
Demographics	х	х								
Medical History/Inclusion/Exclusion Criteria	х	х								
SCID – Diagnostic Interview		Х								
SITBI – Suicidality Interview		Х	Х	Х	Х	Х	Х	Х	Х	Х
Randomization			Х							
Administer Study Agent E2 (or placebo) Patch				х	х		Х	х		
Dispense Study Agent P4 (or placebo) Pills				Х	Х		Х	Х		
Height/Weight				Х			Х			
Pregnancy and Drug Tests				Х			Х			
E2/P4/ALLO/Inflammatory Gene Expression Blood Measure				х	х	х	х	х	х	
CESD - Depression Self-Report				Х	Х	Х	Х	Х	Х	
BHI – Hopelessness Self-Report				Х	Х	Х	Х	Х	Х	
STAI – Anxiety/Threat Sensitivity Self-Report				х	Х	х	Х	Х	Х	
SSES – Negative Social Appraisals Self-Report				х	х	х	х	х	х	
UPPS-P – Impulsivity/Inhibitory Control Self-Report				х	Х	х	Х	Х	Х	
FT-IRAP – Hopelessness Task				х	х	х	Х	х	х	
SAR-IAT – Negative Social Appraisal Task				х	Х	х	Х	Х	Х	
SST – Inhibitory Control Task				Х	Х	Х	Х	Х	Х	
DPT – Threat Sensitivity Task				Х	Х	Х	Х	Х	Х	
Adverse Event/Side Effect Evaluation				Х	Х	Х	Х	Х	Х	
Parasympathetic Activity – Respiratory Sinus Arrythmia				Х	Х	Х	Х	Х	Х	

*Condition 3, Visits 7-9 are identical to Condition 2, Visits 4-6.

7.4 JUSTIFICATION FOR SENSITIVE PROCEDURES

Placebo control is required to demonstrate unique effects (vs. expectancy effects) of hormones on indices of suicidality.

Ongoing Assessment of Suicidality

The PI ([name]) is a clinical psychologist with nine years of experience in risk assessment and empirically supported treatment of chronic suicidality (e.g., Dialectical Behavior Therapy); [name], whose office is adjacent to [name], is an experienced clinical psychiatrist with clear expertise in suicide risk assessment and management. These clinical qualifications will allow the PI and [name], the prescribing physician for the study, to carefully assess and manage any emergent changes in imminent suicide risk.

The available literature³ indicates that *participants in research studies do not generally become acutely upset in response to the psychological assessments conducted in the present study.* If participants do become upset during an assessment, they will be reminded of their right to discontinue participation, and mood changes or suicidality will be assessed and managed using the University of Washington Risk Assessment and Management Procedure (**UWRAP**), the suicide risk management protocol recommended by NIH in the context of RCTs for mood disorders.

7.5 CONCOMITANT MEDICATIONS, TREATMENTS, AND PROCEDURES

All concomitant prescription medications taken during study participation will be recorded. For this protocol, a prescription medication is defined as a medication that can be prescribed only by a properly authorized/licensed clinician. Medications to be reported are concomitant prescription medications, over-the-counter medications and non-prescription medications.

7.5.1 PRECAUTIONARY MEDICATIONS, TREATMENTS, AND PROCEDURES

There are no medications that are prohibited for concomitant use with the study agents, with the exception of any hormonal preparations (that are exclusionary).

7.6 PROHIBITED MEDICATIONS, TREATMENTS, AND PROCEDURES

There are no prohibited medications or procedures except hormonal preparations, which are exclusionary. However, inclusion/exclusion criteria exclude those reporting ongoing treatment for a chronic (non-psychiatric) medical condition, as well as excluding those with a positive enrollment drug screen for opioids, methamphetamines, or cocaine, since recreational use of these drugs may indicate heightened risk of a suicide attempt.

7.7 PROPHYLACTIC MEDICATIONS, TREATMENTS, AND PROCEDURES

Not applicable.

7.8 RESCUE MEDICATIONS, TREATMENTS, AND PROCEDURES

Not Applicable.

Hospitalization will serve as a "rescue treatment" should imminent suicidal risk emerge.

7.9 PARTICIPANT ACCESS TO STUDY AGENT AT STUDY CLOSURE

Participants will not be provided access to study medications following the termination of this study; as noted above, this is a mechanistic experimental study and not a treatment study.

8 ASSESSMENT OF SAFETY

The safety of the study and its participants (as described in 2.3.1) will be monitored via (1) Supervising physician [name]./Ph.D. (hormone-related AEs) and [name]. (mood and suicide-related AEs) as well as (2) a Data and Safety Monitoring Board (DSMB).

AEs will be assessed daily during the telephone contacts in the two administration conditions, and will be assessed weekly at laboratory visits. All AEs will be reported immediately to the PI and [name], who will determine severity and next steps.

A DSMB of three experts outside the PI's department will evaluate AEs that are submitted during scheduled reviews (every 6 months). The DSMB will be composed of MDs and PhDs from relevant disciplines, including clinical psychology, gynecology, and endocrinology.

Although not expected given the doses and duration of hormone exposure, the DSMB will, during scheduled reviews, specifically evaluate the frequency of AEs related to the hormonal RCT. The DSMB will specify the tables and data it wishes to have presented to it at all meetings, including but not limited to, moderate to severe side effects and all serious adverse events. **DSMB review of this study will occur every six months**. At these meetings the DSMB will also review data from participants who have been discontinued by study staff or who have withdrawn or dropped out of the study, and the reasons for discontinuation. The DSMB will also identify if any study procedures should be altered or stopped in the event of an indication of harm to participants attributable to the study interventions. The DSMB will evaluate issues of participant safety as well as the adequacy and integrity of accumulating data, review of enrollment data, and making recommendations regarding safety.

8.1 SPECIFICATION OF SAFETY PARAMETERS

8.1.1 DEFINITION OF ADVERSE EVENTS (AE)

Adverse event means any untoward medical occurrence associated with the use of an intervention inhumans, whether or not considered intervention-related (21 CFR 312.32 (a)).

8.1.2 DEFINITION OF SERIOUS ADVERSE EVENTS (SAE)

Serious adverse event or serious suspected adverse reaction. An AE or suspected adverse reaction is considered "serious" if, in the view of either the investigator or sponsor, it results in any of the following outcomes: death, a life-threatening adverse event, inpatient hospitalization or prolongation of existing hospitalization, or a persistent or significant incapacity. Important medical events that may not result in death, be life-threatening, or require hospitalization may be considered serious when, based upon appropriate medical judgment, they may jeopardize the patient or subject and may require medical intervention to prevent one of the outcomes listed in this definition.

*Notable examples of serious adverse events in the present study include development of a venous thromboembolism or suicide attempt.

8.1.3 DEFINITION OF UNANTICIPATED PROBLEMS (UP)

CLEAR 2 Study Protocol: Hormones and Suicide Risk, Version 9, 07-02-2020, Page 37 of 64

OHRP considers unanticipated problems involving risks to participants or others to include, in general, any incident, experience, or outcome that meets all of the following criteria:

- Unexpected in terms of nature, severity, or frequency given (a) the research procedures that are described in the protocol-related documents, such as the IRB-approved research protocol and informed consent document; and (b) the characteristics of the participant population being studied;
- Related or possibly related to participation in the research ("possibly related" means there is a reasonable possibility that the incident, experience, or outcome may have been caused by the procedures involved in the research); and
- Suggests that the research places participants or others at a greater risk of harm (including physical, psychological, economic, or social harm) than was previously known or recognized.

This study will use the OHRP definition of UP.

8.2 CLASSIFICATION OF AN ADVERSE EVENT

8.2.1 SEVERITY OF EVENT

For AEs not included in the protocol defined grading system, the following guidelines will be used to describe severity.

- **Mild** Events require minimal or no treatment and do not interfere with the participant's daily activities.
- **Moderate** Events result in a low level of inconvenience or concern with the therapeutic measures. Moderate events may cause some interference with functioning.
- Severe Events interrupt a participant's usual daily activity and may require systemic drug therapy or other treatment. Severe events are usually potentially life-threatening or incapacitating.

8.2.2 RELATIONSHIP TO STUDY AGENT

For all AEs, [name] will urgently collaborate with [name] to determine the AE's causality based on temporal relationship and clinical judgment. The degree of certainty about causality will be graded using the categories below.

Definitely Related – There is clear evidence to suggest a causal relationship, and other possible contributing factors can be ruled out. The clinical event occurs in a plausible time relationship to drug administration and cannot be explained by concurrent disease or other drugs or chemicals. The response to withdrawal of the drug (dechallenge) should be clinically plausible. The event must be pharmacologically or phenomenologically definitive, with use of a satisfactory rechallenge procedure if necessary.

Probably Related – There is evidence to suggest a causal relationship, and the influence of other factors is unlikely. The clinical event occurs within a reasonable time after administration of the drug, is unlikely to be attributed to concurrent disease or other drugs or chemicals, and

CLEAR 2 Study Protocol: Hormones and Suicide Risk, Version 9, 07-02-2020, Page 38 of 64

follows a clinically reasonable response on withdrawal (dechallenge). Rechallenge information is not required to fulfill this definition.

Possibly Related – There is some evidence to suggest a causal relationship (e.g., the event occurred within a reasonable time after administration of the trial medication). However, other factors may have contributed to the event (e.g., the participant's clinical condition, other concomitant events). Although an AE may rate only as "possibly related" soon after discovery, it can be flagged as requiring more information and later be upgraded to "probably related" or "definitely related," as appropriate.

Unlikely to be related – A clinical event whose temporal relationship to drug administration makes a causal relationship improbable (e.g., theevent did not occur within a reasonable time after administration of the trial medication) and inwhich other drugs or chemicals or underlying disease provides plausible explanations (e.g., theparticipant's clinical condition, other concomitant treatments).

Not Related – The AE is completely independent of study drug administration, and/or evidenceexists that the event is definitely related to another etiology. There must be an alternative, definitive etiology documented by [name] or [name].

8.2.3 EXPECTEDNESS

[name] will collaborate with [name] to make determinations about whether an AE is expected or unexpected. An AE will be considered unexpected if the nature, severity, or frequency of the event is not consistent with the risk information previously described for the study agent.

8.3 TIME PERIOD AND FREQUENCY FOR EVENT ASSESSMENT AND FOLLOW-UP

The occurrence of an AE or SAE may come to the attention of study personnel during study visits and interviews of a study participant. All AEs including local and systemic reactions not meeting the criteria for SAEs will be captured on the appropriate documentation. Information to be collected includes event description, time of onset, clinician's assessment of severity, relationship to study product (assessed only by those with the training and authority to make a diagnosis), and time of resolution/stabilization of the event. All AEs occurring while on study must be documented appropriately regardless of relationship. All AEs will be followed to adequate resolution.

Pre-existing medical conditions are exclusionary for participation in the trial, with the exception of psychiatric conditions. Any psychiatric condition or symptom that is present at the time that the participant is screened, including mood symptoms and suicidal *ideation*, will be considered as baseline and not reported as an AE. However, if the study participant's condition or symptom deteriorates significantly with regard to the severity or impact of the symptom on the participants functioning or safety (as determined by Drs. [name] and [name]) at any time during the study, it will be recorded as an AE. UPs will be recorded in the data collection system throughout the study.

Changes in the severity of an AE will be documented to allow an assessment of the duration of the event at each level of severity to be performed. AEs characterized as intermittent require documentation of onset and duration of each episode.

The PI will record all reportable events with start dates occurring any time after informed consent is obtained until 7 (for non-serious AEs) or 30 days (for SAEs) after the last day of study participation. At each phone call and study visit, study staff will inquire about the occurrence of AE/SAEs since the last visit. All AEs will be immediately reported to the PI, who will respond (psychiatric AEs) or consult with [name] as soon as possible (for medical AEs). Events will be followed for outcome information until resolution or stabilization.

8.4 REPORTING PROCEDURES

8.4.1 ADVERSE EVENT REPORTING

Study staff will screen for all AEs at each telephone call and study visit. [name] will be on call for all visits and telephone calls to ensure that emergent mood deterioration or suicide risk can be immediately handled by a licensed clinical psychologist with experience in suicide risk assessment ([name]) using the LRAP/UWRAP protocol (the tool recommended by NIH for clinical trials with suicidal subjects). Medical/physical AEs will be discussed as soon as possible with [name].

The PI [name] (in consultation with [name]) will review all protocol data at monthly meetings, including enrollment and retention statistics and aggregate reports of side effects/AEs. As the contact PI, [name] will be the one responsible for reporting any severe AEs to the IRB and DSMB within 1 week. Since we are employing a marketed pharmaceutical product (i.e., a non-IND study), unexpected Serious AEs will be also be reported to the FDA Medwatch Program. The NIMH program officer will be notified of any study modifications or suspension imposed by the DSMB or local IRB in response to an AE.

8.4.2 SERIOUS ADVERSE EVENT REPORTING

The PI ([name]) will complete a SAE Form within the following timelines:

• All deaths and immediately life-threatening events, whether related or unrelated, will be recorded on the SAE Form and submitted to the DCC/study sponsor within 24 hours of site awareness. See **Section 1, Key Roles** for contact information.

All SAEs will be followed until satisfactory resolution or until the PI deems the event to be chronic or the adherence to be stable. Other supporting documentation of the event may be requested by the DSMB or study sponsor and will be provided as soon as possible. The study sponsor will be responsible for notifying FDA of any unexpected fatal or life-threatening suspected adverse reaction as soon as possible but in no case later than 7 calendar days after the sponsor's initial receipt of the information.

8.4.3 UNANTICIPATED PROBLEM REPORTING

Incidents or events that meet the OHRP criteria for UPs require the creation and completion of an UP report form. It is the site investigator's responsibility to report UPs to their IRB and to the study sponsor. The UP report will include the following information:

- Protocol identifying information: protocol title and number, Pl's name, and the IRB projectnumber;
- A detailed description of the event, incident, experience, or outcome;
- An explanation of the basis for determining that the event, incident, experience, or outcomerepresents an UP;
- A description of any changes to the protocol or other corrective actions that have been taken or are proposed in response to the UP.

To satisfy the requirement for prompt reporting, UPs will be reported using the following timeline:

• All UPs will be reported to the IRB, the DSMB, and to the study sponsor within 1 week of the investigator becoming aware of the event.

8.4.4 EVENTS OF SPECIAL INTEREST

Not applicable.

8.4.5 REPORTING OF PREGNANCY

Pregnancy will result in immediate withdrawal from the study and a breaking of the blind to [name]; [name] will oversee appropriate clinical care, including supervised hormonal discontinuation.

8.5 STUDY HALTING RULES

Administration of study agent will be halted when three serious AEs* determined to be "probably related" (i.e., with new onset during study patches/pills) are observed. The PI will immediately notify the DSMB when this occurs. The DSMB will notify the study sponsor and investigators immediately when the third severe event is reported and enrollment screens will stop accepting new study participants. The DSMB will request the statistical analyses and tables that they wish to review, and these will be prepared by an unblinded biostatistician associated with the study. All requested documentation will be provided to the DSMB. The DSMB will convene an ad hoc meeting by teleconference or in writing as soon as possible. The DSMB will provide recommendations for proceeding with the study to the PI and the NIH. The study sponsor will inform all appropriate regulatory agencies of the temporary halt and the disposition of the study.

*Statistically, the most likely examples of serious adverse events in the present study include development of a venous thromboembolism or a suicide attempt during an experimental phase of the study.

CLEAR 2 Study Protocol: Hormones and Suicide Risk, Version 9, 07-02-2020, Page 41 of 64

8.6 SAFETY OVERSIGHT

Safety oversight will be under the direction of a DSMB composed of individuals with the appropriate expertise as determined by their regulatory guidelines. The DSMB will meet every 6 months to assess safety and efficacy data in each condition of the study. The DMSB will operate under the rules of an approved charter that will be written and reviewed at the organizational meeting of the DSMB. At this time, each data element that the DSMB needs to assess will be clearly defined. The DSMB will provide its input as required to NIMH.

9 CLINICAL MONITORING

Clinical site monitoring is conducted to ensure that the rights and well-being of human subjects are protected, that the reported trial data are accurate, complete, and verifiable, and that the conduct of the trial is in compliance with the currently approved protocol/amendment(s), with GCP, and with applicable regulatory requirement(s).

- [name], the project manager, will be responsible for the adequate clinical documentation of all events as described in the current protocol, including data verification and backup.
- Evaluation of the safety of the study will take place via the DSMB every six months and as needed when AEs emerge (see sections above).

10 STATISTICAL CONSIDERATIONS

10.1 STATISTICAL AND ANALYTICAL PLANS

There will be no formal SAP. The PI will conduct all analyses at the end of the trial.

10.2 STATISTICAL HYPOTHESES

Hypotheses. For suicidal desire and suicidal action capacity—our primary endpoints)—we predict that perimenstrual increases in suicidal desire and action capacity (Lab 2 – Lab 1 within each condition) will be larger in the placebo (natural E2 + P4 withdrawal) condition and experimental E2 stabilization (P4 withdrawal) condition than in the experimental P4 stabilization (E2 withdrawal) condition. The associated null hypothesis is that there will be no difference in the perimenstrual increase in suicidality across conditions. For our secondary endpoints, including hopelessness, negative social appraisals, reduced inhibitory control, and threat sensitivity, we predict the same pattern of results.

There are no "efficacy" endpoints in the present trial since it is mechanistic and not a treatment study.

10.3 ANALYSIS DATASETS

An intent-to-treat dataset will be utilized. The study statistician will use a carry-forward approach to evaluate the within-person condition effect using this intent-to-treat sample.

CLEAR 2 Study Protocol: Hormones and Suicide Risk, Version 9, 07-02-2020, Page 42 of 64

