Primary Windows of Comparison for Hypothesis Testing. To test whether prevention of P4 withdrawal (in Condition C) reduces the perimenstrual increase in suicide risk, **primary** hypothesis tests will compare degree of suicide risk (as measured with self-report, tasks, and interviews) during the perimenstrual weeks of each condition (days +7 to +22). **Secondary** analyses will examine Condition C, testing whether tapered withdrawal from exogenous P4 around days +16 to +22 causes "shifted"/"postponed" perimenstrual risk.

Hypotheses/Analytic Plan. It is hypothesized that Condition A (E2/P4 withdrawal under placebo) and Condition B (P4 withdrawal under E2 stabilization) will BOTH be associated with heightened perimenstrual suicidality, but that Condition C (E2 withdrawal under P4 stabilization) will significantly reduce perimenstrual increases in suicidality. We also hypothesize that a steeper slope of ALLO withdrawal, calculated across the lab ALLO measures in each condition, will mediate the more deleterious effects of P4 withdrawal conditions. Multilevel models will be used (repeated observations nested within individuals) to predict daily or weekly repeated suicidality and mediator outcomes from a within-person condition factor (and, if appropriate, the interaction of condition and day). Mediation by degree of ALLO withdrawal will be tested by estimating a 95% CI for the indirect effect of condition (focal predictor) on suicide risk outcomes (dependent variable) via the slope of ALLO change across the perimenstrual phase (mediator). **Power Analysis**. For primary hypothesis tests, 80% power to detect a conventionally medium-sized effect of condition (f = .25) is achieved with 24 participants¹¹⁷. To allow for attrition and improve generalizability and power, we propose to include 30 participants.

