4.2.1 PRIMARY ENDPOINT

The primary endpoints (described below) of this mechanistic study are suicidal ideation and planning score differences between placebo condition and stabilization conditions on the SITBI measure. These were chosen given their strong predictive validity in epidemiological studies.

(1) Mean Within-Person Condition Differences (7 final placebo days – 7 final stabilization days) of SITB Suicidal Ideation subscale score

CLEAR 2 Study Protocol: Hormones and Suicide Risk, Version 9, 07-02-2020, Page 14 of 64

(2) Mean Within-Person Condition Differences (7 final placebo days – 7 final stabilization days) of SITB Suicidal Planning subscale score

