6.1.9 DURATION OF THERAPY

The planned duration of active treatment is 14 days. All days in which participants use patches and pills will be utilized in multilevel modeling analyses, which accommodate unbalanced/missing data.

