10.4.2 ANALYSIS OF THE PRIMARY EFFICACY ENDPOINT(S)

Primary and secondary endpoints are operationalized above (i.e., mean within-person differences between conditions) for the daily SITB suicidal ideation and planning subscales (primary endpoints) as well as the daily UPPS-P impulsivity, PROMIS anxiety, CESD depression, BHI hopelessness, and SSES rejection sensitivity subscales (secondary endpoints).

Analyses will proceed identically for all outcomes listed above. First, we will calculate each subject's mean daily rating (via phone) on the outcome measure *during* each condition.

Second, we will utilize repeated measures ANCOVA to examine the within-person condition effects. Covariates (medicines, BMI, age) will be examined and included. These analyses will be conducted on the intent-to-treat dataset.

If necessary due to violations of model assumptions, we will utilize similar nonparametric tests.

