10.5 SAMPLE SIZE

An unlimited number of potential participants will be screened. 60 females will be enrolled in the study, with the goal of 40 participants completing the study.

Power analyses are described below; alpha is set at .05, power at 80%. The null hypothesis is no link between the study experimental condition and risk for suicidal ideation, intent, and planning; the alternate hypothesis is that hormone stabilization in the experimental condition will prevent flux in these suicide-related outcomes. Because no previous studies have examined the impact of experimental hormones on suicidality, we have conducted power analyses using existing effect sizes on related constructs (e.g., BPD features).

Power Analysis. For primary hypothesis tests, 80% power to detect a conventionally mediumsized effect of condition (f = .25) is achieved with 24 participants¹¹⁷. To allow for attrition and improve generalizability and power, we propose to include 40 participants in the final sample.

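### The carry-forward rule in 10.3 is undefined and conflicts with the multilevel models in 4.1 and 6.1.9; if values cross conditions, 20 losses of 60 shrink each contrast by 0% to 33%, depending on when participants leave

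*Combined protocol and SAP*

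**What the plan says.** Section 10.3 specifies an intent-to-treat dataset and adds: "The study statistician will use a carry-forward approach to evaluate the within-person condition effect using this intent-to-treat sample". Nothing else in the document defines the rule.

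Section 10.4.2 describes the primary analysis in two steps. First, "we will calculate each subject's mean daily rating (via phone) on the outcome measure" within each condition; second, "we will utilize repeated measures ANCOVA to examine the within-person condition effects", with medicines, BMI and age as covariates, on the intent-to-treat dataset.

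Two other sections describe a different analysis. Section 4.1 states: "Multilevel models will be used (repeated observations nested within individuals"), applied to daily or weekly outcomes. Section 6.1.9 says that all days on patches and pills "will be utilized in multilevel modeling analyses, which accommodate unbalanced/missing data".

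Section 10.1 closes off a later document that could settle the matter: "There will be no formal SAP. The PI will conduct all analyses at the end of the trial". On expected loss, 10.5 states: "60 females will be enrolled in the study, with the goal of 40 participants completing the study".

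**The concern.** Filling missing values and modelling only the observed ones are different analyses, and the plan names both. For a participant who never starts a condition, carry-forward has two readings.

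1. Values cross conditions. The only on-treatment score available comes from another condition, so the rule writes a zero difference into a within-person contrast.
2. Values are carried only within a started condition. The rule then supplies nothing for a condition that was never started. A conventional repeated measures ANCOVA needs complete rows and drops her.

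The first reading biases the quantity that 4.2.1 defines as primary, namely "suicidal ideation and planning score differences between placebo condition and stabilization conditions on the SITBI measure". The second does not deliver the intent-to-treat analysis promised in 10.3. Loss is a planned scenario, and 5.4.1 allows termination for severe changes in suicidality, which is the construct being measured.

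**Working it through.** **Inputs from the documents.** 60 enrolled and 40 completers, hence 20 losses (10.5). Six orders (10.6.1), described as counterbalanced (4.1, 10.4.6). Randomisation at the enrollment visit, before any study agent (7.3.2), so loss before condition 1 is possible. Two withdrawals after randomisation in the preceding study (2.1), with 30 analysed (2.1) or 30 retained (5.3). Two-sided alpha .05 (10.4.1). f = .25 (10.5).

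**Assumed.** Timing of loss; equal numbers per order; loss unrelated to outcome (steps 1 to 5); no period effect; within-person correlation 0.5; normal scores. The preceding study's denominator is taken as 30 or 32.

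**The plan's own figure.** 10.5 gives 24 participants for 80% power at f = .25. With a noncentral F and λ = N·m·f²/(1−ρ), three conditions at ρ = 0.5 need 28 (24 gives 74.1%). The figure 24 is reached at ρ of about 0.56, or with four measurements at ρ = 0.5. The documents state neither, so 24 can be neither confirmed nor refuted. Nothing below depends on it.

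**Step 1: what a filled participant contributes.** Let a, b, c be the true condition means. Lost after condition 1, all three values are equal and every contrast is 0. Lost after condition 2, the third condition takes the second's value, and A−C becomes:

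- ABC: a−b; ACB: a−c; BAC: 0
- BCA: 0; CAB: a−c; CBA: b−c

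Mean = 3(a−c)/6 = 0.5(a−c). By symmetry A−B and B−C are also halved.

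**Step 2: shrinkage for 20 losses.** Shrinkage = 1 − (F + 0.5H)/(60 − L), where F and H are the numbers with three and two conditions observed and L the number lost before condition 1. A started condition counts as observed, ignoring attenuation within it.

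| Timing of the 20 losses | Calculation | Shrinkage |
|---|---|---|
| All after condition 1 | 1 − 40/60 | 33% |
| 10 after condition 1, 10 after condition 2 | 1 − (40+5)/60 | 25% |
| All after condition 2 | 1 − (40+10)/60 | 17% |
| 10 before condition 1, 5 after condition 1, 5 after condition 2 | 1 − (40+2.5)/50 | 15% |
| 5 before condition 1, 5 during each of conditions 1, 2 and 3 | 1 − (45+2.5)/55 | 14% |
| All during condition 3 | 1 − 60/60 | 0% |
| All before condition 1 | 1 − 40/40 | 0% |

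**Step 3: the preceding study's rate.** 0.5 × 2/30 = 3.3% to 2/30 = 6.7%; with 32, 3.1% to 6.3%.

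**Step 4: effect on the interval when values cross conditions.** With A = B > C and SD 1, the SD of the means is d√2/3. Setting this to .25 gives d = 0.53. Simulation with 60 participants, 10 per order:

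| Case | A−C estimate (true 0.53) | Model SE / empirical SE | 95% coverage |
|---|---|---|---|
| 17% | 0.44 | 0.124 / 0.123 | 89% |
| 25% | 0.40 | 0.117 / 0.115 | 80% |
| 33% | 0.35 | 0.110 / 0.104 | 65% |

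The two SEs agree closely, so the intervals have about the right width but the wrong centre. At 4 of 60 lost, coverage stays near 95%. In these three cases type I error is 4.7% to 5.6% and power for the condition effect 93% to 97%.

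**Step 5: the alternatives.** Forty completers only: estimate 0.53, SE 0.157, coverage 94% to 95%, power 93% to 94%. A mixed model on observed condition means: 0.53, SE 0.140 to 0.152, coverage 95% to 96%, power 95% to 98%.

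**Step 6: loss related to outcome.** Each SD of score is assumed to multiply the weight for loss by 2.7. If the last observed score drives loss, filling keeps 83%, 74% and 66% of A−C in the three cases, and the mixed model still gives 0.53. If the next, unobserved score drives it, filling keeps 83%, 73% and 65%, and the mixed model gives 0.50 to 0.51. The completers-only analysis was not run in this setting.

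**The case against.** The strongest reply is that the practical effect may be small. Twenty losses is an allowance, not a forecast. The only observed loss rate in the documents gives 3% to 7%, although that study lasted 4 months and this one lasts 6 to 7. Carrying may be meant only within a condition, which is unbiased under random loss. Under either reading type I error holds and power stays above 90%. All of this stands and limits the point to the estimate, its interval and the definition of the analysis.

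Three stronger readings are tempting and not supported.

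- A reader might take 17% as the least shrinkage that 20 losses can cause. That would require every loss to fall between conditions, after condition 1 or 2. Randomisation precedes a baseline cycle, and the triggers in 5.4.1 may well arise while a condition is running. Both timings lower the figure, to 0% at the extreme.
- A reader might infer that incomplete participants must be excluded under the second reading. Section 10.4.2 names no estimation method, and a likelihood fit would keep them. Exclusion is what the conventional method does, not something the plan states.
- A reader might infer an inflated false-positive rate because the choice of analysis is left open. No section says that the analysis will be chosen by its result, and the day-level models of 4.1 and 6.1.9 are not specified well enough to simulate. No figure for this is justified.

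**Conclusion.** The point holds and should be fixed before analysis. The one filling rule in the plan has no stated unit or boundary. It either pulls every primary contrast toward zero or, under conventional ANCOVA, fails to give an intent-to-treat analysis, and it sits beside an unreconciled multilevel plan.

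The size is conditional. If values cross conditions, the average shrinkage is 0% to 33% at 20 of 60 lost, set by the timing of loss, and 3% to 7% at the preceding study's rate. The lowest coverage, 65%, needs all 20 to leave after condition 1. The coverage figures also rest on normal scores, correlation 0.5 and A = B > C, although 10.4.1 itself expects non-normal suicidality scores. The halving in step 1 needs only balanced orders, no period effect and loss unrelated to outcome.

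**What to change.** Delete carry-forward from 10.3. In 10.4.2 name one primary analysis: a likelihood-based mixed model on all observed data from randomised participants, with no filling, fixed effects for condition and period, the medicines, BMI and age covariates already planned, and a random person effect. State whether its unit is the condition mean or the day, and make 4.1, 6.1.9 and 10.4.2 agree. Require that any nonparametric or other non-normal fallback accept incomplete rows.

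Report, by order, how many participants contribute 0, 1, 2 and 3 conditions. Add one sensitivity analysis for outcome-related loss, given 5.4.1. One option is to impute missing condition means from the primary model, shift them in condition C only and then in A and B only, and report the shift at which the A−C interval reaches 0. For scale, if all 20 are lost after condition 2, each condition is missing for (20 × 1/3)/60 = 0.11 of participants, so a 1 SD shift moves A−C by 0.11 SD. If all are lost after condition 1 it is (20 × 2/3)/60 = 0.22 SD.

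The cost is rewording four sections and one extra analysis. No new data are needed.
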